4.0 BACKGROUND & RATIONALE

4.1 Rationale

Recent clinical trials have shown great promise for a range of immunotherapy drugs, including anti-PD-1 therapy, in a variety of cancers. These therapies all share the common approach of activating the patient’s immune system towards the tumor. This differs from conventional cytotoxic systemic therapies which non-specifically target dividing cells, including immune cells. For example, anti-PD-1 drugs such as pembrolizumab target PD-1, a receptor expressed on immune cells, which mediates an immunosuppressive effect when allowed to interact with its ligands PDL1 and/or PDL2. Since many tumors express PDL1/PDL2, therapies such as pembrolizumab block this interaction and have the potential to unmask the tumor to the immune system. When successful, this leads to an immune infiltration of the tumor and ultimately tumor cell death.

From the radiological perspective, following cancer response to immunotherapy presents unique challenges compared to conventional cytotoxic chemotherapies. Studies of anti-CTLA4 therapy with ipilimumab in melanoma revealed that a significant subset of responding tumors may exhibit non-traditional patterns of response that can confound interpretation on CT (computed tomography).¹ An example of a non-traditional response is the initial increase in size of the tumor over the course of several months with a later decrease in tumor size. In these cases, the initial increase in size of the tumor is thought to be on the basis of tumor infiltration by immune cells and can be mistaken for tumor growth on CT. Another example of a non-traditional tumor response to immunotherapy is a decrease in the size of the primary tumor with the development of new small lesions. This pattern has also been observed to correspond with favorable outcome in the setting of immunotherapy but would be considered disease progression by conventional measures.

An apparent increase in tumor burden that later resolves or decreases has been called a flare response, and is hypothesized to result from a transient immune-cell infiltrate in the tumor stroma. Several studies provide support for this hypothesis, including a case study of an ipilimumab-treated patient with apparent progressive disease at 12 weeks, in which the histological analysis of a lung nodule demonstrated a T-cell infiltrate, extensive necrosis, and no residual tumor cells.² Thus, a different set of response criteria have been developed, termed immune-related response criteria (irRC), that incorporate the possibility of a transient flare response, as well as a delayed immune response, into the assessment.^{1,3} While irRC has

been shown to be an improvement over conventional RECIST (Response Evaluation Criteria In Solid Tumors) in the setting of immunotherapy, irRC still does not accurately identify all responders and non-responders. This is partly due to the fact that morphological changes to the tumor from immunotherapy can take several months to manifest. Thus, a more timely and accurate measure of response to immunotherapy is needed.

FDG PET/CT as a marker of cancer and inflammation:

2-Deoxy-2-[¹⁸F]fluoro-D-glucose (FDG) is an ¹⁸F analogue of glucose that serves as a PET radiotracer of cellular metabolism. FDG enters the cell through cell surface glucose transporters and becomes trapped within the cell following enzymatic phosphorylation by hexokinase. For decades, FDG has been employed to detect cancer exploiting a phenomenon known as the Warburg effect in which most malignancies preferentially produce ATP through a boost in extra-mitochondrial glycolysis, rather than mitochondrial oxidative phosphorylation, despite aerobic conditions. This metabolic switch, termed aerobic glycolysis, has a greater rate of glucose utilization albeit overall lower ATP yield, and provides the generation of key carbon precursors needed for the synthesis of nucleic acids, phospholipids, fatty acids, cholesterol and porphyrins.⁴ As a result of the increased rate of glycolysis characteristic of the Warburg effect, most malignancies utilize more glucose (and FDG) than their non-transformed neighboring cells, which has led to the use of FDG PET/CT as a highly sensitive and moderately specific tool for the detection of occult metastatic disease.

It has recently been recognized that immune activation results in a similar cellular metabolic switch from oxidative phosphorylation to aerobic glycolysis. This occurs with both the innate and adaptive immune activation. For example, when activated using TLR ligands or pro-inflammatory cytokines, neutrophils, dendritic cells, and macrophages have been demonstrated to switch their metabolism from oxidative phosphorylation to aerobic glycolysis.⁵ Similarly, following TCR stimulation, lymphocytes increase glucose utilization by several orders of magnitude and switch glucose metabolism from oxidative phosphorylation to aerobic glycolysis.^{6,7} Interestingly anti-inflammatory subpopulations of both the innate and adaptive immune system, such as M2 macrophages, regulatory T cells and quiescent memory T cells, demonstrate a predominant use of oxidative phosphorylation rather than aerobic glycolysis as opposed to their inflammatory counterparts such as activated macrophages and T-helper 17 cells.⁸

The upregulation of aerobic glycolysis in immune activation is readily visualized with FDG PET/CT imaging. Inflammatory conditions such as infection, rheumatoid arthritis and sarcoidosis yield intense avidity for FDG that compares with or exceeds that of most malignancies.^{9,10} In fact, a significant limitation to the use of FDG PET/CT in cancer restaging has been interference of the tumor FDG signal by post-therapeutic inflammatory tissues including surgical changes, talc pleurodesis, and radiation therapy.¹¹

In this study we propose utilizing FDG PET/CT to assess the immunotherapy response by detecting the superimposed increased metabolism within the tumor presented by a therapy-induced infiltrating population of glucose avid activated immune cells. Of note, a flare

phenomenon has been described in several cancer types following therapy; in patients with breast cancer on endocrine therapy, a clinical flare response was identified in 4 of 17 responders and 1 of 34 nonresponders, and an FDG PET flare response was seen in 15 of 17 responders and none of the 34 nonresponders.¹² These results suggest that FDG PET is more sensitive and specific for detecting a flare response compared to clinical criteria, and the results also suggest that a flare response is predictive of response to therapy.

FDG PET/CT studies are typically performed at approximately 12 weeks following the initiation of

pembrolizumab, and the probability of seeing a flare response on these clinical studies is very low; this is supported by data presented at ASCO in 2014, in which 3.6% of patients with melanoma

demonstrated a flare response on imaging ($\geq 25\%$ increase in tumor burden) at 12 weeks. We propose looking for a flare response at about 3 weeks following the start of immunotherapy. The choice of this time point is considered appropriate for the activation and expansion of immune cells and is supported by data on pembrolizumab in non-small cell lung cancer, which revealed that circulating cytotoxic T cells specific to tumor neoantigens peak at around 3 weeks from the initiation of therapy (Figure 1).¹³ Additional data on pembrolizumab in multiple other tumor types also found that activated cytotoxic T cells peak at around 3 weeks.¹⁴

[figure not shown]

Figure 1: Neoantigen-specific T cell response to pembrolizumab in non-small cell lung cancer. In a study by Rizvi *et al*, the magnitude of the neoantigen (HERC1 P3278S) reactive CD8+ T cell response was measured in peripheral blood of patients with non-small cell lung cancer receiving pembrolizumab by determining proportion of CD8+ T cell population in serially collected autologous peripheral blood lymphocytes recognizing the HERC1 P3278S neoantigen (ASNASSAAK) before and during pembrolizumab treatment. In this study the neoantigen specific T cells begin to peak at day 21 of anti-PD1 therapy. (Nayer A. Rizvi *et al*. Science 2015;348:124-128.)

No significant change is expected in the tumor's inherent basal glycolytic activity over the short interval between the baseline FDG PET/CT and the 3 week PET/CT. Therefore we hypothesize that the flare response will be able to be visualized with FDG PET/CT by detection of a superimposed burst of tumoral glycolytic activity resulting from immunotherapy induced immune infiltration. If successful, this study will help to determine the ideal time point for visualization of the flare response, test the potential for the flare response to serve as a biomarker for detecting an early response to therapy, and contribute to our understanding of pembrolizumab's mechanism of action.

In addition, studies in human tumor tissue are needed to define the mechanism of action of PD-1 inhibition, and provide an explanation for observed changes in tumor FDG uptake. In this study we propose collecting pre- and post- treatment tumor tissue in which the post-treatment tumor tissue is acquired within 7 days following the 3 week PET/CT. We also propose acquiring blood samples pre-therapy, and at serial time-points during therapy (including a 1 week sample, which is earlier than other studies have explored to date). Analysis of these samples will include, but is not limited to, serum cytokines, chemokines, and T cell markers, and tumor-infiltrating lymphocytes (TILs) and macrophages; some of

these studies will be performed upon receipt of additional funding. Of note, some of these studies will be informed by, and/or modeled after the current study at Penn titled, “A Phase Ib Tissue Collection Study of Pembrolizumab (MK-3475) in Subjects with Resectable Advanced Melanoma.” This data will be correlated to patient response as well as changes in tumor FDG uptake. Thus, we expect the proposed study to generate mechanism of action data, and help identify factors that predict response to treatment with PD-1 inhibition, which may allow for more strategic development of combination immune therapy strategies, and ultimately may help to increase objective response rates to immune therapy in melanoma and other tumor types.

4.1.1 Dose Rationale and Risk/Benefits Assessment

2-Deoxy-2-[¹⁸F]fluoro-D-glucose (FDG) is FDA approved for imaging in clinical oncology, and has been extensively used in oncologic PET imaging with no evidence of pharmacological effect. No adverse events (AEs) have been reported in the large number of published studies of human experience for FDG at the dose to be used in this study. In this study we will administer approximately 15 mCi of FDG according to the standard procedures used for clinical FDG PET/CT at the Hospital of the University of Pennsylvania.

Risk/Benefit

Participants will undergo up to two additional FDG PET/CT examinations for the purposes of this study. This will be in addition to other clinically indicated CT and/or PET/CT examinations. FDG is a positron emitting radiopharmaceutical. As such, it poses an intrinsic radiation exposure risk. However, when administered in low tracer doses as a PET imaging agent, as described in this protocol, this risk is felt to be extremely small. In addition to the radioactive FDG tracer, a low-dose CT of the chest, abdomen and pelvis is typically performed with the FDG PET/CT for the purpose of anatomical registration and attenuation correction of PET images. There are no separate diagnostic CT scans performed as part of this scan. FDG PET/CT scans are a standard clinical procedure for patients with metastatic melanoma. This research involves exposure to radiation that could affect a fetus or pregnant woman, due to this risk a urine pregnancy test will be performed for women of childbearing potential at the time of screening. Women who are pregnant at the time of screening will not be included in this study.

The dose will be delivered intravenously by skilled clinical professionals who typically administer FDG for clinical purposes; venous cannulation is a routine clinical procedure that carries minimal risks when performed by trained personnel. It is possible that bruising, dizziness or fainting could occur in some subjects. There is a risk of phlebitis or infection, which is very remote. Also, the PET/CT scan takes place in a small, enclosed space and therefore can be uncomfortable for some people with claustrophobia or musculoskeletal disorders (such as arthritis). Subjects will be made as comfortable as possible and staff will be available throughout the imaging to address any discomfort.

No psychological, social or legal risk is expected. While loss of confidentiality is possible, it is felt to be very unlikely due to the small number of professionals involved in the study with

knowledge of this information. All clinicians and research staff involved are well trained in HIPAA practices. There is no anticipated additional financial risk to the patient due to participation in this study since the two additional study FDG PET/CT's, 1 week blood draw (if performed), and post-therapy tumor biopsy (if performed) will be paid for through study funds. The clinical restaging FDG PET/CT examinations and pre-therapy tumor biopsy (if performed) will be paid for through the patient's insurance as per routine clinical care for their cancer. Additional blood draws described in this protocol outside of the 1 week sample will be paid for by the Penn Melanoma Tissue Collection Program.

The risk to the patient is felt to be minimal with only the added radiation considered the likely risk posed to the patient. It is not unusual for oncologic patients to receive multiple radiological tests, including multiple PET/CT scans, in the course of clinical management and the addition of two FDG PET/CT scans is not considered to add a large risk to the subject. This study proposes the addition of two PET/CT scans to the patient's care. This study also proposes the addition of one tumor biopsy to the patient's care; this procedure carries a low risk of bleeding or infection at the biopsy site, thus the additional risk to the patient from this procedure is felt to be minimal.

There is no anticipated benefit to study subjects as a result of their participation in this study. There is potential benefit to general society if FDG PET/CT proves to be a useful imaging agent for detecting an early response to immunotherapy for cancer, or helps in the understanding of pembrolizumab's mechanism of action.

4.1.2 Rationale for Endpoints

4.1.2.1 Primary Endpoint

Objective response to therapy at 6 months, based on imaging and the clinical evaluation of the patient, is an acceptable primary endpoint in this prospective, observational cohort study of FDG PET/CT as an early measure of response in patients with advanced metastatic melanoma. Response will be determined by RECIST version 1.1. While either CT or MRI may be utilized, as per RECIST 1.1, CT is the preferred imaging technique in this study. Patients will be categorized as responders (i.e., complete response or partial response) or nonresponders (stable disease or progressive disease).

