1.0 TRIAL SUMMARY

Abbreviated Title	Imaging the flare response from pembrolizumab with FDG PET/CT.
Trial Phase	Correlative
Clinical Indication	Patients with advanced metastatic melanoma who are starting pembrolizumab.
Trial Type	Prospective observational cohort study.
Type of control	No control.
Route of administration	n/a
Trial Blinding	None
Treatment Groups	n/a
Number of trial subjects	30 evaluable subjects
Estimated enrollment period	1 year
Estimated duration of trial	2 years
Duration of Participation	6 months
Estimated average length of treatment per patient	n/a

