6.0 TRIAL FLOW CHART

6.1 Study Flow Chart

	Screening Phase	Baseline FDG PET/CT ⁴	1 st Post-therapy FDG PET/CT	Tumor Tissue Collection ⁵	2 nd Post-therapy FDG PET/CT ⁶
Scheduling window relative to pembrolizumab initiation:		< 4 weeks prior	3 weeks after (\pm 3 weeks)		> 10 weeks after
Administrative Procedures					
Informed Consent	X				
Inclusion/Exclusion Criteria	X				
Demographics and Medical History	X				
Clinical Procedures/Assessments					
Review Adverse Events ¹			X	X	
Laboratory Procedures/Assessments: analysis performed on site					
Pregnancy Test – Urine or Serum β -HCG	X				
Tumor Imaging and Assessment of Disease					
FDG PET/CT ²		X	X		X
Tumor Biopsies/Archival Tissue Collection/Correlative Studies Blood					
Archival or Newly Obtained Tissue Collection	X			X	
Correlative Studies Blood Collection ³					

¹Adverse events related to the research PET/CT will only be assessed for the period of time from the injection of FDG to the completion of the imaging exam. AEs related to the clinical treatment will not be collected or reported as part of this study.

²All FDG PET/CT scans will be performed as per routine clinical procedure.

³Less than 65 mL of blood will be collected after initiation of pembrolizumab according to the following schedule: weeks 0, 1, 3, 6, 9, 12, 15, and at 1 year; specimens will be processed and stored according to the Penn Melanoma Program tissue collection Standard Operating Procedure. The week 1 blood sample will be collected only for the purposes of this study. If blood samples cannot be collected they will be omitted and not considered a protocol deviation.

⁴This scan will usually be performed as a research exam. Occasionally, it may be performed as a clinically indicated restaging exam, which may occur prior to consent and enrollment in this study.

⁵Tumor tissue is to be collected within 7 days after the 1st Post-therapy FDG PET/CT. The biopsy techniques preferred for this study include core biopsies or surgical biopsies. The same biopsy techniques should be used as routinely used for a given tumor lesion/location and specimens will be processed and stored according to the Penn Melanoma Program

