7.1.5 Image Interpretation

Static images will be reconstructed using standard procedure and analyzed by visual inspection and standardized uptake value (SUV) analysis. The tumor avidity, as estimated by the SUVmax, of the primary tumor and up to 5 metastatic lesions will be measured on each FDG PET/CT scan. Patients will be grouped into responders (partial/complete response) and nonresponders (stable disease or progressive disease) based on RECIST. Patients will also be grouped based on a positive flare response (greater than 20% increase in SUVmax) or negative flare response (less than 20% increase in SUVmax). An exploratory tumor-by-tumor FDG PET/CT response analysis will be performed for the primary tumor and up to 5 metastatic lesions in each patient. Changes in FDG uptake within immune related tissues (lymph nodes, spleen, bone marrow, and thymus) will also be measured as an exploratory objective using SUVmax and SUVmean.

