8.0 STATISTICAL CONSIDERATIONS

8.1 Design:

This is a pilot correlative study for patients with metastatic melanoma receiving pembrolizumab on a standard regimen. The intent of this study is to evaluate FDG PET/CT as an early measure of response to immunotherapy. Tumor FDG uptake will be measured at baseline and at 3 and >10 weeks after initiation of pembrolizumab. 30 evaluable patients will be enrolled; evaluable implies that the patient had baseline and week 3 FDG PET/CT scans. This study will also include serum and tissue sampling for immune biomarkers.

8.2 Objectives:

The primary objectives are to:

1. Determine the distribution of changes from baseline in tumor FDG uptake on PET/CT at 3 weeks and >10 weeks after initiation of pembrolizumab.
2. Test for the association between change in tumor FDG uptake on PET/CT at 3 weeks and objective response (RECIST).

The secondary objectives are to:

1. Based on change in FDG uptake at 3 weeks, determine which patients have FDG “flare.”
2. Test for the association between FDG flare (yes/no) and objective response.
3. Test for the association between FDG flare and progression-free and overall survival.
4. Test for correlation between change in FDG uptake and levels of immune biomarkers in serum and tissue.
5. Test for association between changes in immune biomarkers in serum and tissue with objective response, progression-free survival, and overall survival.

8.3 Endpoints:

1. Objective response is defined by RECIST. The clinical evaluation takes place at 3 months per standard pembrolizumab regimens. Patients will be categorized as responders (complete response or partial response) or nonresponders (stable disease or progressive disease).

2. The maximum standardized uptake value (SUVmax) will be analyzed for all tumor sites. Immune-related tissues will be analyzed with SUVmax and SUVmean.
3. Studies have shown that the baseline test/re-test variability is 15-20%. Thus, FDG “flare” will likely be defined by >20% increase in tumor FDG uptake at 3 weeks. This definition may be modified for the observed distribution of changes in tumor FDG uptake on our study.
4. Progression-free and overall survival are defined in Section 4.1.2.
5. Immune biomarkers (see Section 7.1.2.3).

8.4 Plans for Data Analysis:

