This is a pilot correlative study of FDG PET/CT imaging to evaluate early response to immunotherapy. We will first begin with a descriptive analysis. For continuous variables, we will generate graphs and descriptive statistics (e.g., means, standard deviations, medians and inter-quartile range). Categorical variables will be described by frequencies, proportions and 95% exact confidence intervals. Change in tumor FDG uptake will be closely examined. It is likely that change in tumor SUVmax >20% will be classified as a FDG “flare” and the number of patients with a flare will be computed.

Next, associations between change in tumor FDG uptake with clinical outcomes will be conducted. Change in tumor FDG uptake at 3 weeks will be compared between responders and nonresponders by a two sample t-test. Also, objective response rates will be compared between patients with or without FDG “flare” by Fisher’s exact test.

PFS and OS will be estimated by the method of Kaplan and Meier. Median values and 95% confidence intervals will be calculated. PFS and OS will be compared between patients with or without FDG “flare” by the log rank test. Cox regression may be used to assess the effect of continuously scaled measurements of FDG change. For all survival analyses, a landmark analysis will be performed. Here, PFS or OS are defined from a landmark, which is 3 weeks after initiation of pembrolizumab. The landmark method is necessary because the change in tumor FDG uptake is known at 3 weeks. Serum and tissue biomarkers will be correlated with change tumor FDG uptake, using Pearson correlation or Spearman’s correlation, as appropriate. Within-patient pre-/post-treatment changes in biomarkers will be evaluated by paired Student’s t-test or Wilcoxon signed ranks test, as appropriate. We will test for an association between post-/pre-treatment fold change in immune biomarkers in serum and tissue and objective response, progression-free survival, and overall survival using logistic regression (for response) and Cox regression (for time-to-event outcomes) using landmark survival analysis.

8.5 Sample Size Justification:

The target is 30 evaluable patients, which may require up to 35 enrolled patients. Based on our clinical experience, we assume a 50% objective response rate, thus there will be 15

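### The primary endpoint is response at 6 months in Section 4.1.2.1, but Section 8.3 attaches a 3-month evaluation to the same responder split, and nothing reconciles the two

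*Combined protocol and SAP*

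**What the plan says.** Two places give a time for the assessment of response.

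- **Section 4.1.2.1, Primary Endpoint:** "Objective response to therapy at 6 months, based on imaging and the clinical evaluation of the patient, is an acceptable primary endpoint". Response is by RECIST 1.1, and patients are split into complete or partial response against stable or progressive disease.
- **Section 8.3, Endpoints, item 1:** objective response is by RECIST, followed by "The clinical evaluation takes place at 3 months per standard pembrolizumab regimens" and then the same split.

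The sections that use the split give no time for it.

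- **Section 7.1.5:** "Patients will be grouped into responders (partial/complete response) and nonresponders (stable disease or progressive disease) based on RECIST".
- **Section 8.4, primary test:** "Change in tumor FDG uptake at 3 weeks will be compared between responders and nonresponders by a two sample t-test".
- **Section 8.4, flare comparison:** "objective response rates will be compared between patients with or without FDG" flare, by Fisher's exact test.
- **Section 8.5:** a 50% objective response rate, hence 15 against 15, with no time attached.

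Three other entries touch on timing. The trial summary has "Duration of Participation 6 months". Section 4.1 says "FDG PET/CT studies are typically performed at approximately 12 weeks following the initiation of" pembrolizumab. The flow chart in Section 6.1 puts the last scan at "> 10 weeks after" the start of treatment, with no upper limit.

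**The concern.** Responder status defines both groups in the primary comparison of FDG change at 3 weeks. It is also the outcome in the Fisher test of flare against response and in the logistic regressions of response on biomarkers. If its time is open, those groups are open too. Someone working from Section 8 would classify patients at 3 months, and someone working from Section 4.1.2.1 at 6 months; each would be following the plan. The study is unblinded, so the choice could be made after the FDG changes are known.

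The protocol's own rationale gives reason to expect the two times to disagree for some patients. Section 4.1 describes tumours that enlarge over months and later shrink, and says that size changes under immunotherapy can be slow to appear. A patient could be a nonresponder at 3 months and a responder at 6.

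The problem is limited in scope. Primary objective 1 (the distribution of FDG changes), the PFS and OS analyses, the correlations of biomarkers with FDG change and the paired biomarker tests do not use the responder split.

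**Working it through.** **1. Does any section settle the time?**

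| Place | Time given for response |
|---|---|
| 4.1.2.1 Primary Endpoint | 6 months |
| 8.3 Endpoints, item 1 | evaluation at 3 months, next to the same split |
| 3.1 and 8.2 Objectives | none |
| 7.1.5 Image Interpretation | none |
| 8.4 Plans for Data Analysis | none |
| 8.5 Sample Size Justification | none |
| 11.2 RECIST appendix | none |
| 1.0 Trial Summary | 6 months of participation, not linked to response |
| 6.1 Flow Chart | last scan after more than 10 weeks, which fits either time |
| 7.1.4.2 Clinical Follow-up | visit timing left to the treating physician |

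Nothing says that 3 months is only a first look, that best response is meant, or which section takes precedence.

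**2. The plan's own power figure.** Inputs from Section 8.5: 15 against 15, difference 1.0 SD, one-sided 5%, two-sample t-test. With 28 degrees of freedom the critical value is 1.701. The noncentrality is 1.0 / √(1/15 + 1/15) = 2.739. The noncentral t distribution gives power 0.848, against the stated 84%. The figure reproduces, so the power statement is not in error.

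**3. Effect of a different response rate alone.** The response rate may differ between the two times. Keeping the 1.0 SD difference and 30 patients, noncentrality = 1.0 / √(1/n₁ + 1/n₂):

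| Responders / nonresponders | Rate | Noncentrality | Power |
|---|---|---|---|
| 15 / 15 | 50% | 2.739 | 84.8% |
| 12 / 18 | 40% | 2.683 | 83.5% |
| 10 / 20 | 33% | 2.582 | 80.9% |

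This effect is small.

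**4. Effect of patients changing group (illustration).** Assume that the 1.0 SD difference holds for the 15/15 split at one time, that one patient is in the other group at the other time, and that this patient keeps the FDG distribution of the group left behind. The groups are then 14 and 16, with one of the 16 drawn from the other distribution.

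- Mean difference: 1 − 1/16 = 0.9375.
- Variance of the mixed group: 1 + (1/16)(15/16) = 1.0586.
- Pooled variance: (13 × 1 + 15 × 1.0586) / 28 = 1.0314.
- Noncentrality: 0.9375 / √(1.0314 × (1/14 + 1/16)) = 2.522.
- Power: 0.793. Simulation (200,000 runs) gives about 0.80.

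By symmetry the result is the same whichever way the patient moves. Simulation with two and three patients moved in one direction gives about 74% and 68%. The documents give no reclassification rate, so none of these counts is an estimate.

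**The case against.** The strongest reply is that the two sections do not directly contradict each other. Section 8.3 does not say that response is determined at 3 months; its sentence can be read as a description of routine care. Section 4.1.2.1 is the only text headed Primary Endpoint, the trial summary sets participation at 6 months, and Section 8.3, item 4, refers back to Section 4.1.2 for PFS and OS, as if endpoint definitions live there. This makes 6 months a reasonable reading. It does not close the matter: the cross-reference covers only PFS and OS, while item 1 restates response itself and gives 3 months as the only response time in the statistical section.

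A second reply is that few patients may change category. The pattern of growth and later shrinkage in Section 4.1 comes from ipilimumab studies. The same section puts flare on imaging at 12 weeks at 3.6% of patients with melanoma, which is 0.036 × 30 ≈ 1 patient. This limits how many early increases might later reverse. It does not cover slow responders, with stable disease at 3 months and partial response at 6.

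A third reply is that this is a pilot observational study with a correct power figure. That bears on the size of the consequence, but the groups of the one powered test still need a definition.

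**Conclusion.** The concern holds. The current text gives two times next to the same responder split and no rule for choosing between them, so the groups of the primary t-test are not uniquely defined. This conclusion rests on the text alone.

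The numerical consequence is secondary and cannot be estimated from the documents. A changed response rate by itself costs about 1 to 4 points of power over rates from 40% down to 33%. Reclassification of a single patient would take power from 84.8% to about 79%, on the unstated assumptions that the 1.0 SD difference belongs to one time and that the moved patient keeps the FDG distribution of the group left behind. The sample size is not shown to be wrong. The point should be fixed before analysis because it governs the only powered test.

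**What to change.** Reconcile Sections 4.1.2.1, 7.1.5 and 8.3 to one prespecified RECIST 1.1 response time for the responder groups; the choice is the sponsor's. If it is 6 months, say in Section 8.3 that 3 months is only the first routine evaluation. Tie the 50% response rate in Section 8.5 to the chosen time. Report response at the other time as a labelled sensitivity analysis.

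Because visit timing is not mandated, add an assessment window around the chosen time and a rule for classifying patients with no assessment inside it. Otherwise those patients' group would remain undefined.

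The cost is protocol and SAP wording; the change itself requires no added scans or patients. The downside is that some patients may lack an assessment near the chosen time, and the 50% rate and stated power may need to be restated.
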